(Aim 2b) Functional Ability will be assessed with The Six-Minute Walk Test (6MWT)⁴⁶ (10 minutes) which measures the distance walked on a hard flat surface in 6 minutes. A section of 30 meters will be marked off using two orange cones and participants will be asked to walk at a comfortable pace for a 6-minute period between the cones while being timed. Test-retest reliability has been documented as high as .90 at baseline, .88 at 18 weeks, and .91 at 43 weeks⁴⁷ for older patients with heart failure.⁴⁷ Participants may have different levels of current activity. In order to control for this, step-data will be adjusted for baseline.

(Aim 2c) Health Outcomes (10 minutes). Resting blood pressure will be measured on each participant in a seated position using a Withings blood pressure cuff by the RA who will be a registered nurse. The RAs will be blinded to the study groups. The RAs will also obtain a radial pulse (heart rate) over a 60-second count while the participant remains seated. Weight for determining Body Mass Index (BMI) will be measured without shoes and in light clothing and be calculated to the nearest 0.1 pound using a digital scale that will be calibrated prior to testing.⁴⁸ Height will be measured without shoes using a self-retracting tape measure and rounded to the nearest 0.1 cm. Body mass index (BMI; kg/m²) will be calculated as [mass (lb)/ height (in)² x 703]. Waist circumference (WC) will be obtained by measuring the individual's circumference halfway between the iliac crest and the lower anterior ribs with the person standing upright during expiration.⁴⁹

(Aim 2d) Quality of Life. The Short Form Health Survey (SF-12) (5 minutes) (Appendix C.2) contains 12 questions that explore a person's physical (functional) and mental (well-being) health over the previous 4 weeks.⁵⁰ The SF-12 includes 8

Study Title: Increasing Activity Post-Kidney Transplant with SystemCHANGE™

IRB Protocol Number: 2017B0084

Approval Date: 10-22-18

NCT03191630

Version: 08/28/2018

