domains—Physical Functioning, Role-Physical, Bodily Pain, General Health, Vitality, Social Functioning, Role-Emotional, and Mental Health⁵⁰—and uses a Likert-like scale from 1 to 3 for the physical function items which focus on bodily pain, social function, vitality, mental, and general health perceptions. A dichotomous yes/no scale is used for emotional and physical role function items.⁵¹ Physical and mental component scores, ranging from 0 (lowest level of health) to 100 (highest level of health), are derived from the individual items and will be used as study outcomes. The questionnaire has been found to have high internal consistency (Cronbach's alpha coefficients of .72 to .89) and adequate test-retest reliability ($r = .73\text{-.86}$).^{51,52}

D. Detailed study procedures

All study data will be entered directly into electronic research forms using Research Electronic Data Capture system (REDCap, surveys, and other instruments by study participants and research staff that will automatically upload into REDCap. Similarly, mobile activity tracker data (steps) aggregated by the secure Fitabase will also upload into REDCap. The REDCap Admin will provide technical support for project duration.

Overview of Intervention and Control Groups

Intervention and control groups will be enrolled in the study in the same manner, receive the same instruction on use of the Fitbit Charge HR, and have the same number of study contacts. Study procedures include group sessions at the OSU Transplant Clinic with 10-12 participants for 6 months and a 6-month maintenance phase without contact from study personnel until month 12. One research assistant will be assigned to the intervention group and one to the control group.

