Intervention Group Active Phase, Group Session 1 (1 hour, 20 minutes) [name] and a research assistant (RA) will demonstrate proper Fitbit Charger HR activity tracker use, set up the smartphone application, and assist entry of daily step goals into the smartphone application. Fitbits will be set up with Gmail accounts with unique unidentifiable codes. Participants will be taught how to sync to their smartphone and retrieve data from their Fitbit. Participants will perform a return demonstration to confirm they can apply the activity tracker to their wrist, access their Fitbit account, and charge the activity tracker. One week following this session, participants will be called to troubleshoot problems and be encouraged to increase their step goal 5% each month (total phone time 15 minutes).

Figure 3. Intervention/Control Group Timeline

Study Title: Increasing Activity Post-Kidney Transplant with SystemCHANGE™

IRB Protocol Number: 2017B0084

Approval Date: 10-22-18

[figure not shown]
NCT03191630

Version: 08/28/2018

Intervention Active Phase, Group Session 2 (1 hour) This session will begin with brief introductions of research staff and study participants followed by a session overview. The first topic to be reviewed will be Fitbit activity tracker reports (Appendix B.2). Participants will be oriented to the report, including the steps being monitored, the range of dates for the report, and general information (number of monitored days, number of daily steps taken, and number of activity minutes per day). Consistent with SystemCHANGE™, phrases such as “opportunities for improvement” and “possibilities for doing better” will be employed when discussing the report with participants. Questions will be solicited and answered before proceeding to delivery of the SystemCHANGE™ component of the intervention.

A PowerPoint presentation will briefly introduce SystemCHANGE™ component of the intervention followed by participants being divided into small groups of 5 each. In these small groups and with the aid of a workbook (see Appendix B.3), RAs and the PI will guide participants through the 4 steps of SystemCHANGE™.

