toward improvement will be discussed and demonstrated. In this session and throughout the Active Phase of the intervention, participants will be encouraged to look beyond personal motivation and explore their life routines and the people who shape those routines.

Intervention Active Phase, Group Sessions 3-7 (1 hour/session) Participants' progress will be reviewed using the Plan-Do-Study-Act Model³³ that employs small participant-designed experiments. Prior to each session, the participants' activity tracker reports will be given to them (Appendix B.2) and reviewed during the group session. Participants will be asked to "Tell me what you are learning about physical activity, and do you think changes that you have made to your routines are changing the level and consistency of your physical activity? Do you need to make other changes to your physical activity routines?" If the participant and RA agree that changes are warranted, participants will be encouraged to identify and try another solution. At the last monthly meeting, participants will be asked to describe their improvements and be encouraged to continue using the activity tracker for the next 6 months during the maintenance phase (see Figure 3).

Intervention Maintenance (6 months) At the final monthly session, participants will be instructed to continue with intervention and reminded that the research team will not be in contact for 6 months, after which time there will be a final group session.

Control Group

Control Active Phase, Group Session 1

Session 1 for the control group will be identical to the Intervention with the only exception being that participants in the control group will NOT be asked to increase their step goal 5% each month based on the step-data we receive from baseline to week 1.

Control Active Phase Group Session 2-7, (1 hour/ session) Session 2 will be used to troubleshoot and discuss any problems with the Fitbit activity trackers. In subsequent sessions, educational information about healthy living as a transplant recipient will be presented, including topics such as diet, taking medication, risk for skin cancer, gastrointestinal side effects, dental care, and new onset post-transplant diabetes. The meeting time will be equivalent to those of the intervention group

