Control Maintenance Phase, (6 months) Identical to the intervention group; at the final month 7, group session participants will be reminded to continue to use the Fitbit activity tracker and that the research team will not be in contact with them for 6 months, after which time there will be a final group session.

Study Measures: In addition to

demographic and

inclusion/exclusion

screening (including cognitive screening), the following measures will be collected: perception of activity trackers use (Six-Minute Walk Test, blood pressure, heart rate, body mass index, waist circumference, and Short Form Health Survey (SF-12)

An iPad will be used to

administer all questions that will enable direct data entry into REDCap. RAs will provide

Table 6. Measurement Timeline

Data Collection	Baseline	Data Collection Timeline											
		Months											
	1	2	3	4	5	6	7	8	9	10	11	12	
Basic Demographic	X												
Cognitive Screening	X												
Perception of Activity Tracker		X	X	X			X					X	
SF-12	X			X		X						X	
Number of Steps	X			X		X						X	
Six-Minute Walk Test	X			X		X						X	
Blood Pressure	X			X		X						X	
Heart Rate	X			X		X						X	
BMI	X			X		X						X	
Waist Circumference	X			X		X						X	

Study Title: Increasing Activity Post-Kidney Transplant with SystemCHANGE™

IRB Protocol Number: 2017B0084

Approval Date: 10-22-18

NCT03191630

Version: 08/28/2018

assistance as needed by reading questions to participants and assisting with indicating responses on the iPad. Outcome data from both study groups will be collected at the appropriate sessions as shown in the Table 6.

1. See document for details describing what will happen at each intervention group meeting.
2. See document for details describing what will happen at each control group meeting

Retention: Text messages will be sent to participants during months when they are not attending a face-to-face session to provide encouragement and reinforcement for their participation in the study. In addition, phone calls will be made during each month to each participant to provide updates on their progress in the study as well as encouragement and support. Participants who complete the study will be allowed to keep their activity tracker.

E. Internal Validity

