Treatment fidelity⁴³ for both study groups will be assured first, though the use of a scripted manual for each group session will be used during RA training sessions which will include role-playing with simulated participants until competency in delivery of group sessions is demonstrated. A log of the time taken for each group session will be kept to ensure equivalent treatment dose across all sessions. Debriefing will be conducted following each session to identify any areas for improvement. A protocol checklist will be used to ensure that content is completely and consistently covered and all outcome measures are collected at baseline, 1,2, 3, 6, and 12 months.

F. Data Analysis

The overall analytic design is a mixed design model where participants are randomly assigned to one of two intervention or comparison arms. The response over time of the participants will likely be correlated, therefore covariance patterns over time to be considered include compound symmetry, autoregressive, exponential (allows for unequally spaced times) and unstructured. The unstructured covariance pattern allows for less variation in the outcome variable (e.g., days engaged in activities) at baseline—a condition which may occur and will be evaluated.

Aim 1: Perception of activity trackers will be determined by participants' responses to open-end surveys. The responses from these surveys will be analyzed using content analysis to explore narrative responses for each open-ended question for commonalities and placed in emerging patterns or themes.

Aim 2: The test of effectiveness for each intervention arm is assessed by evaluating the treatment group by time interaction with two a priori contrasts (one for each arm) comparing the one-year follow-up mean to the baseline mean (essentially a paired t-test in the context of ANOVA). If an intervention is effective, we expect an initial rapid and sustained increase in the

Study Title: Increasing Activity Post-Kidney Transplant with SystemCHANGE™

IRB Protocol Number: 2017B0084

Approval Date: 10-22-18

NCT03191630

Version: 08/28/2018

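### The protocol calls the RAs who take blood pressure and pulse blinded, but its staffing and session procedures do not support this at months 3, 6 and 12

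*Combined protocol and SAP*

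**What the plan says.** Section III.C, Aim 2c (Health Outcomes) has resting blood pressure measured "using a Withings blood pressure cuff by the RA who will be a registered nurse". The next sentence is "The RAs will be blinded to the study groups", and the one after it gives the RAs the radial pulse as well, counted by hand over 60 seconds.

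Section III.D, Overview of Intervention and Control Groups, sets the staffing: "One research assistant will be assigned to the intervention group and one to the control group". Under Intervention Active Phase, Group Session 2, "RAs and the PI will guide participants through the 4 steps of SystemCHANGE". Under Group Sessions 3-7 the RA is still working on content with each participant: "If the participant and RA agree that changes are warranted, participants will be encouraged to identify and try another solution".

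On where outcomes are collected, section III.D (Study Measures) says "Outcome data from both study groups will be collected at the appropriate sessions as shown in the Table 6", and section III.C says the same. Section III.E (Internal Validity) uses one checklist for delivery and measurement, to "ensure that content is completely and consistently covered and all outcome measures are collected at baseline" and at the later time points. For the end of the study, the Control Maintenance Phase text says "the research team will not be in contact with them for 6 months, after which time there will be a final group session"; the intervention text has the same arrangement.

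The measurement timeline (Table 6) schedules blood pressure and heart rate at baseline and months 3, 6 and 12. Section III.F lists both as secondary outcomes.

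**The concern.** An RA who is attached to one arm and delivers its content knows the allocation of the people in the room. If that RA also takes the follow-up readings, the measurement is not blinded, whatever section III.C says. A report written from this protocol would then claim masked assessment of blood pressure and heart rate that the described procedures do not provide.

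Two distinct things are at stake. The first is expectation: an observer who knows the arm may, without intending to, obtain or record readings that favour it. A hand-counted pulse is the more exposed of the two measures. The second follows from having one RA per arm. If each RA measured only their own arm, any systematic difference between the two observers would be confounded with treatment, and no analysis could separate them. The scripted manual, time log and checklist in section III.E standardise delivery; they mask nobody.

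**Working it through.** The plan gives no figure to reproduce, so the check sets the sections side by side.

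1. **Who measures.** Section III.C gives blood pressure to an RA who is a registered nurse and the pulse to the RAs in the plural. It uses the same term that section III.D uses for session staff, and names no separate assessor.

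2. **What the RAs know.** Section III.D attaches one RA to each arm. RA delivery of intervention content is explicit from session 2 onward. For control sessions 2-7 the text does not say who presents; RA delivery there is an inference from the per-arm assignment and from section III.E, which trains RAs on scripted sessions for both groups.

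3. **Where and when measurement happens.** Sections III.C and III.D put it at the sessions, and section III.E ties it to the session checklist. The month-12 contact is itself a group session. No separate assessment visit or concealment step appears.

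4. **Which visits are affected.** There are four planned readings: baseline and months 3, 6 and 12. Steps 1 to 3 apply to the three follow-ups. Baseline is unsettled. Section III.F places baseline characteristics before randomisation, but section III.B (Recruitment) places consent at the first group meeting, and section III.D describes session 1 under each arm. Session 1 is almost the same in both arms, however. Its one stated difference is encouragement to raise the step goal, which the intervention text places in a phone call a week later. An assessor attached to neither arm could therefore still be blind at session 1.

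5. **Which analyses use the readings.** Section III.F plans a baseline-to-12-month contrast in each arm and 95% confidence intervals for the changes, and extends this to the secondary outcomes. The month-12 blood pressure and pulse readings enter those contrasts directly. Steps per day come from the wristband, and the power calculation is for steps, so neither depends on an RA's reading.

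6. **Why shared measurement helps, and what it leaves.** Suppose RA 1 reads higher than RA 2 by a constant d. At a given visit, let the imbalance be the share of the intervention arm measured by RA 1 minus the share of the control arm measured by RA 1. Then

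   bias in the between-arm difference in change = d × (follow-up imbalance − baseline imbalance).

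   If one RA measures everyone, or both RAs measure equal shares of both arms at every visit, both imbalances are 0 and the bias is d × (0 − 0) = 0. This term would arise even with fully masked observers, so it does not measure the effect of unblinding. Expectation bias is separate, and balancing observers does not remove it. The documents give no value for d and do not say who measures which arm, so no size is computed.

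**The case against.** The strongest reply is that the registered-nurse RA could be a third person attached to neither arm, who takes readings before session content begins. The protocol refers to separate documents describing each session, which are not part of the text reviewed, and Figure 3 is not shown. No arm-specific content is described for the month-12 session. Staffing is also not fixed at two: Group Session 2 has several RAs and the PI working with small groups inside one intervention session, which does not fit one RA per arm. Finally, these are secondary outcomes in a pilot that section III.F says is not powered for differences between arms.

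Much of this stands, and it limits the point. A reader might infer that blinding at months 3, 6 and 12 is impossible. The documents do not support that; they support only that the described procedures do not deliver it. A reader might also infer that each arm is measured by its own RA, or that RAs certainly run the control sessions. Neither is stated.

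The reply does not rescue the sentence. If a third assessor exists, the protocol neither names that person nor separates measurement from the sessions, and the staffing sentence points the other way. The extra RAs in Group Session 2 would mean more staff who know who is in the intervention arm.

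**Conclusion.** The blinding statement in section III.C is not supported by the procedures as written for blood pressure and pulse at months 3, 6 and 12. Baseline is unsettled. This rests on reading RAs as the same staff in sections III.C and III.D, and on the absence of any described masked assessor or separate visit.

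No numerical magnitude is claimed. It is tempting to assume an observer difference and derive a loss of confidence-interval coverage, but such a figure would rest on an invented d and an unstated allocation of observers, and would describe an offset that masking does not remove.

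The point should not be widened to the walk test or the SF-12. The protocol claims no blinding there, so there is no contradiction. Nor does it reach the primary outcome or the stated power. It should be corrected because a property the protocol asserts would otherwise be carried into the report, and correcting it is cheap.

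**What to change.** - Withdraw the blinding sentence. Report blood pressure and pulse as assessed unblinded after randomisation, and state this as a limitation.
- The exception: if there is already an RA who delivers neither arm and measures apart from session content, keep the claim and describe that arrangement in section III.C.
- State who takes blood pressure and pulse in each arm, and whether the baseline readings precede randomisation.
- With existing RAs, do not let each arm be measured only by its own RA. Have the same RA, or both in balanced shares, measure both arms at each visit, and record the RA's ID with each reading. Say in the protocol that this balances observer differences and does not remove expectation bias.

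The first three items are wording only. Shared measurement costs some scheduling work and carries a small contamination risk, because an RA attached to one arm would meet participants from the other; keeping measurement apart from session content limits that risk.

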Study Title: Increasing Activity Post-Kidney Transplant with SystemCHANGE™

IRB Protocol Number: 2017B0084

Approval Date: 10-22-18

NCT03191630

Version: 08/28/2018

I. Objectives

The purpose of this study is to determine the best way to help people that have had a kidney transplant perform daily physical activity. Currently, we do not know the best way to help people who have had a kidney transplant to remember to perform regular physical activity. This study will help us explore how to promote routine daily physical activity.

- (a) Determine if perceptions (usability, sustainability, and acceptability) of activity tracker use differs for older adult KTRs participating in a SystemCHANGETM intervention compared to a control group at 1, 2, 3, 6, &12 months.
- (b) Determine the degree to which a SystemCHANGE™ + activity tracker intervention improves physical activity, health outcomes, and quality of life for older adult KTRs from baseline to 3, 6, & 12 months, compared to a control group using only activity trackers.

II. Background and Rationale

The combination of the SystemCHANGE™ and activity tracker intervention holds promise for increasing and sustaining activity among older kidney transplant recipients. This study will incorporate with an accessible popular device with a simple intervention in a population of kidney transplant recipients who are at particularly high risk of cardiovascular disease and death. The findings from this study would have a significant impact on the lives of these individuals and costs associated with their ongoing care.

We will conduct a randomized study with intervention and control arms. Sixty kidney transplant recipients age 65 and older will be recruited and randomized into two groups. Participants in the intervention group will receive the combination of the SystemCHANGE™ and activity tracker intervention while participants in the control group will use activity trackers only. Intervention and control groups will receive the same instruction on use of the activity tracker, and have the same number of study contacts. Study procedures include group sessions with 10-12 participants for 6 months and a 6-month maintenance phase without contact from study personnel until month 12. Outcome analyses will be conducted at baseline, 1, 2, 3, 6, and 12 months. Outcome measures include perception of activity tracker use, physical activity, functional ability, health outcomes, and quality of life.

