Waist Circumference	X			X		X							X

Form Health Survey (SF-12) (Appendix C.2). An iPad will be used to administer all questions that will enable direct data entry into REDCap. RAs will provide assistance as needed by reading questions to participants and assisting with indicating responses on the iPad. Outcome data from both study groups will be collected at the appropriate

Study Title: Increasing Activity Post-Kidney Transplant with SystemCHANGE™

IRB Protocol Number: 2017B0084

Approval Date: 10-22-18

NCT03191630

Version: 08/28/2018

sessions as shown in the Table 6.

Demographic or Sample Measures: Demographic information will be obtained during the screening phone call and will include: gender, race, marital status, income, education, transplant date, prescribed medications, type of diet, smoking status, and comorbidities.

Outcome Measures: (Aim 1) Perception of activity tracker use (Appendix C.1) (15 minutes) will be assessed using 9 open-ended questions to determine participants' perceptions (usability, sustainability, and acceptability) of using mobile activity trackers. (Aim 2a) Number of steps will be recorded continuously each day by a mobile wristband activity tracker called "Fitbit Charger HR" that will sync data from the participant's cellular phone into the Fitabase each day. Fitabase step-data will be downloaded directly into REDCap. The Fitbit Charger HR uses a 3-axis accelerometer to record activity. The device turns movement (acceleration) of a body into digital measurements (step-data) when attached to the non-dominant wrist. In addition, the Fitbit Charger HR provides information about the frequency, duration, intensity, and patterns of movement to determine the number of steps taken each day. In a study comparing the validity of two activity tracker accelerometers, the Fitbit Charger HR and the Physical Activity Monitor (PAM), the Fitbit Charger HR performed more accurately ($r = .77$) than the PAM ($r = .41$) for measuring energy expenditure.⁴⁴ In another study⁴⁵ with 30 adults, no difference was found between the Fitbit Charger HR for steps counted and actual steps observed ($ICC > .95$).

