numbers of steps/day; a subsequent return to near baseline levels would indicate that the intervention is not effective. To quantify the effectiveness of each arm and compare the effectiveness of the two arms at one-year follow-up, we will compute 95% confidence intervals of the changes in the primary outcome variable. The same approach will be used to quantify the effectiveness of the intervention and control groups on the secondary outcome variables. For Aim 2, the primary outcome will be the number of steps per day; secondary outcomes include distance traveled in 6 minutes, health outcomes (blood pressure, heart rate, body mass index, waist circumference) and quality of life (SF-12). Baseline characteristics of participants will be ascertained prior to randomization and all outcomes measured at baseline, 3 months (Follow-up 1), 6 months (Follow-up 2) and 12 months (Follow-up 3). A total of 60 participants will be randomized to either the SystemCHANGE™ + activity tracker intervention or activity tracker control group. Thus, the study has a classical repeated-measures design. Power calculations are based on two-sided t-tests with type-I error rates of 0.05. Effect sizes within arm will be small with standardized differences ranging from 0.37 to 0.58; we assumed a correlation between repeated measures of 0.7. While we used changes from baseline to 12 months to calculate power, we will analyze data for this aim by evaluating the average number of steps/day at baseline and at each follow-up. Results will be analyzed based on intention-to-treat. Using means and standard deviations for accelerometer-based numbers of steps per day from Dontje and colleagues,⁷ we estimate the activity tracker control group to record 6326 ± 2906 steps/day at baseline and 7562 ± 3785 steps/day at 12-months follow-up. In the context of repeated measures ANOVA, using a t-test within arm to detect change from baseline to 12-months, power is 0.575. Because no data exist for determining the effect on steps/day of the SystemCHANGE™ + activity tracker intervention, we assumed that the differences between the means of the two arms at 12 months might conservatively be between 346 and 662 steps/day. Thus, we expect the intervention group to record 6326 ± 2906 steps/day at baseline and between 7908 ± 3785 and 8224 ± 3785 steps/day at 12-months follow-up. Using a within arm t-test, power is 0.798 to 0.918. Change from baseline in each arm will quantify the effectiveness of each in improving the primary outcome. Although this study is not powered to detect differences between the arms at 12 months, we will be able to compare the relative effectiveness of each arm at one-year follow-up and will compute 95% confidence intervals of the changes in outcome variables. We expect that each of these confidence intervals will include the mean of the comparison intervention. If differences between interventions are detected, we expect that the difference will be attributable to (1) fewer numbers of steps/day at baseline compared to the Dontje study⁷ and/or (2) a larger effect on the number of steps/day of the SystemCHANGE™ + activity tracker intervention at 12 months. Data loss due to participant failure to complete all measures is a serious concern in every clinical investigation. Any missing data will be identified at the time of collection and rectified by asking participants to provide the necessary information. However, because subjects have the right to refuse to answer questions (informed consent), we will code null values differently from 'refuse to answer' and 'not applicable'. We will also explore demographics of participants for the effects of influencing outcomes. Missing step-data will occur when participants forget to wear or charge devices overnight; we will identify these missing data prior to the group visit so participants can give information on the reasons for missingness.

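### Objective (a) asks whether perceptions of the tracker differ between the randomised arms, but the Aim 1 analysis contains no comparison by arm or visit

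*Combined protocol and SAP*

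**What the plan says.** Section I, objective (a), poses a question for months 1, 2, 3, 6 and 12: whether perceptions (usability, sustainability, acceptability) "of activity tracker use differs for older adult KTRs participating in a SystemCHANGETM intervention compared to a control group".

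Section III.C, under Outcome Measures (Aim 1), gives the only instrument: perception "will be assessed using 9 open-ended questions". No score, scale or coded variable is defined. Outcome data are to be collected from both groups, and the measurement timeline shows no baseline assessment of perception.

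Section III.F gives Aim 1 two sentences. The first names the data source: "Perception of activity trackers will be determined by participants' responses to open-end surveys". The second says the answers will be "analyzed using content analysis to explore narrative responses for each open-ended question for commonalities and placed in emerging patterns or themes".

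Two other statements in III.F refer to the arms. The section opens with: "The overall analytic design is a mixed design model where participants are randomly assigned to one of two intervention or comparison arms". Under Aim 2, to quantify each arm's effectiveness and to "compare the effectiveness of the two arms at one-year follow-up, we will compute 95% confidence intervals of the changes in the primary outcome variable". Secondary outcomes are then handled likewise.

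**The concern.** The objective is a between-arm question at five visits. The stated analysis looks for what answers to each question have in common. Its output is a set of themes, with no step that sets one arm beside the other or one visit beside another, and no rule for judging whether perceptions differ.

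This leaves one of two stated objectives without a planned route to an answer. Any comparison between the arms would have to be devised later, possibly after the answers have been read, when the choice of themes, visits and form of contrast is open. Using content analysis on open-ended answers is not the fault. What is missing is the step from themes to a comparison.

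**Working it through.** The plan gives no sample size, power or effect size for Aim 1, so there is no figure to reproduce. The check is whether any part of the plan supplies the comparison that objective (a) needs.

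**1. What the objective needs.** Both arms, five visits, and some contrast of perceptions between arms (section I).

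**2. What the Aim 1 analysis supplies.** Themes for each question. Arm, visit, a coded variable and a comparison are all absent (III.F, Aim 1).

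**3. Whether another statement fills the gap.**
- *Opening design statement of III.F.* It mentions the two arms, but leads only to candidate covariance patterns for correlated repeated outcomes. Those cannot be applied to free text that has not been turned into a variable.
- *Aim 2 contrasts and intervals in III.F.* The listed outcomes are steps per day, six-minute walk distance, blood pressure, heart rate, body mass index, waist circumference and SF-12. Perception is not among them. The Aim 2 approach rests on change from baseline, and perception has no baseline measurement. The Aim 2 visits are baseline, 3, 6 and 12 months, which is not the visit set in objective (a).

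Neither fills the gap.

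**4. Whether the data could answer the objective.** Yes. Both randomised groups are asked the questions, and the objective names the visits. Only the analysis step is missing.

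**5. Precision of the comparison proposed under the fix.** These figures describe the remedy, not the size of the defect. Assumptions: 30 per arm, no dropout, each theme coded as mentioned or not, and the same prevalence p in both arms. The 60 participants are stated; 1:1 allocation is not.

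Half-width of the 95% interval = 1.96 × √(2p(1 − p)/30)

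| Assumed p | Calculation | Half-width |
|---|---|---|
| 0.5 | 1.96 × √(0.50/30) | 0.253 |
| 0.3 | 1.96 × √(0.42/30) | 0.232 |
| 0.2 | 1.96 × √(0.32/30) | 0.202 |

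The enrollment schema in III.B sums to 4 + 16 + 3 + 9 = 32 for intervention and 3 + 15 + 2 + 8 = 28 for control. At p = 0.5 that gives 1.96 × √(0.25/32 + 0.25/28) = 0.254, so the split hardly matters.

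**6. Chance findings.** If one theme were tested at 0.05 at each of five visits, treated as independent, the chance of at least one false positive would be 1 − 0.95⁵ = 0.23. Independence is a simplification, since the same people answer each time. Content analysis will normally yield more than one theme, which adds further comparisons.

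**The case against.** The strongest reply is that this is a qualitative component of a single-center pilot. Objective (a) promises no test or estimate, and a structured contrast of themes between groups can legitimately address whether perceptions differ, without numbers. The primary outcome for Aim 2 is steps per day, and III.F already concedes that the study is not powered for between-arm differences at 12 months. With half-widths near 25 points, an added comparison will seldom be conclusive.

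Much of this stands. A qualitative contrast by arm and visit would count, and the stakes are modest. But the plan does not provide for that contrast either. Nor is lack of power a reason for silence: III.F accepts low power for Aim 2 and still commits to reporting intervals.

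Two further cautions also stand, and they shape the remedy. With open-ended questions, a theme that is not mentioned may still be perceived, so a difference in mentions may partly reflect how much people say. And many themes over five visits will produce some intervals that exclude zero by chance.

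A reader might also infer that repeated answers from one person will be counted as if they came from different people. The documents do not support that: the plan proposes no counting of answers, and III.F recognises that responses over time are likely to be correlated.

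**Conclusion.** The mismatch is real. Followed as written, the Aim 1 analysis yields themes and no comparison by arm or visit, so it does not address objective (a), and nothing elsewhere in the plan supplies the comparison. This conclusion comes from the text and needs no numerical assumption.

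A reader might go further and infer that the objective cannot be answered. That goes too far: the answers are collected in both randomised arms, and the gap can be closed by specifying the analysis before the answers are examined.

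The change is worth making because it is cheap and lets the trial address its own question. It does not affect the primary outcome. The precision figure (about ±25 percentage points at 50% prevalence) rests on an assumed prevalence, about 30 per arm and no dropout. It shows that only large differences would stand out, which is why the result should be descriptive.

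**What to change.** Keep the content analysis and add to section III.F, Aim 1, text along these lines:

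> Each participant's answers at each visit will be coded for whether each theme under usability, sustainability and acceptability is mentioned. For months 1, 2, 3, 6 and 12 we will report the proportion of participants mentioning each theme in each randomised arm, and the between-arm difference with its 95% confidence interval. The participant is the unit of analysis. These results are descriptive and exploratory; no claim that perceptions differ will rest on any single unadjusted interval. A theme that is not mentioned will not be interpreted as one that is not perceived.

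If the sponsor does not want this comparison, reword objective (a) as a description of perceptions of tracker use, so that objective and analysis agree.

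Cost: some extra coding of answers that are already being analysed, and tables by visit with wide intervals. No new data or participants are needed. Rewording the objective costs only the edit, but gives up the between-arm question.
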